#### **Step 7: CO2 Measurement**

- At 12-week, the amount of carbon monoxide in the exhaled air for all participants using a CO monitor (Refer to document 5: 12-week follow-up survey)
- The RA will prepare the CO monitor and make sure that there are enough filters (100 filters) for all participants to get measured
- The RA will learn the method of measuring carbon monoxide in the exhaled air
- The RA will record the CO2 measurement results into EpiData along with participant's ID number and other follow-up results

## **2.2 COUNSELOR**

#### **Step 1: Preparation for Counseling Sessions**

- The counselor will train with experts according to the counseling guide (Refer to document 7: counseling guide)
- The counselor will be notified by the RA when there are new intervention participants joining the study (once an ICF has been signed)

### **Step 2: Follow-up Counseling Sessions**

- The counselor will provide counseling sessions at participants' follow-up appointments at the HIV clinic
- The initial counseling session will be face-to-face (20 minutes)
- The next three counseling sessions will be face-to-face ideally, but can be switched to telephone if appropriate (15 minutes each)

### **Step 3: Quality Assurance**

- Counselor will record 10% of all calls for the counseling sessions, these recordings will be transcribed and translated
- The counselor will record any feedback or issues during the sessions and should meet regularly with supervisor for troubleshooting

## **2.3 MATERIALS**

1. Brief screen agreement
2. Adult consent form
3. Baseline survey
4. 8-week follow-up survey
5. 12-week follow-up survey
6. Text messages
7. Counseling guide
8. Self-help manual
9. CO monitor
10. 100 filters for the monitor
11. Tracking spreadsheet
  - a. Spreadsheet with enrollment progress (date and ICF)
  - b. Spreadsheet with contact information (WeChat account names, phone numbers)
  - c. Spreadsheet with text message schedule for each participant
  - d. Spreadsheet of NRT gum usage

## **2.4 STATISTICAL ANALYSIS**

1. Generate mean and standard deviation for demographic variables at baseline (or N and percentage). Run chi-square tests and t-tests for the variables and compare if there is a difference between treatment groups for each of the variables. Variables that are significantly associated with treatment group will be covariates in future analyses.
2. Analyze primary outcome: PPM (CO level) at 12-week. PPM will be a binary outcome: participants have either a PPM level that is less than 8 (success in cessation), or a PPM level of

equal or greater than 8 (no success in cessation). Run an unadjusted logistic regression with 12-week PPM as the outcome and treatment group as the predictor. Run an adjusted logistic regression adjusting covariates

3. Analyze secondary outcomes: 7-day point prevalence abstinence at 8- and 12-week. Run an unadjusted logistic model with 8-week PPA as the outcome and treatment group as the predictor. Run the same logistic model as above but with 12-week PPA. Run an unadjusted logistic model with 8-week PPA as the outcome and treatment group as the predictor, adjusting for covariates. Run the same logistic model as above but with 12-week PPA, adjusting for covariates
4. Analyze other secondary outcomes: quality-of-life, ART adherence, change in smoking quantity, quit attempts.

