### 2.1.3 Randomization

- Study statistician will produce a randomization scheme that is unknown to the RAs and produce 110 envelopes for randomization. Half of the envelopes indicate that participants are assigned to the control group, half of the envelopes indicate that participants are assigned to the intervention group
- After the completion of baseline questionnaire, RA is going to randomly open up an envelope to assign participants to either the control or the intervention group

- The RA is going to input participants' ID number and their assigned group into the data storage system (EpiData)

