### Step 3: Survey Administration and Randomization

- After participants sign the informed consent document, RA will administer the baseline survey, baseline demographics, smoking habits, and other information will be surveyed (Refer to document 3: baseline survey)
- For accurate baseline measurements, the protocol below will be followed:
  - The RA will conduct face-to-face baseline surveying process to all participants

- After participants complete the baseline survey, RA will make sure participant ID is written on the survey
  - Participant's identifiers are going to be removed from the survey and gets stored in another location separated from the survey answers. Survey responses are going to match participants' ID number in EpiData
  - The RA will enter the participant's ID and responses into EpiData
- The RA is going to conduct the randomization process after baseline surveys are completed. Corresponding participant ID and assigned group should be entered into EpiData

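### Covariates are picked by baseline significance tests between randomised arms, so the adjusted models will usually omit predictors of quitting and gain no power

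*Combined protocol and SAP*

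**What the plan says.** Section 2.4, item 1 begins with a baseline table: "Generate mean and standard deviation for demographic variables at baseline (or N and percentage". It continues with "Run chi-square tests and t-tests for the variables and compare if there is a difference between treatment groups for each of the variables" and ends with the selection rule, "Variables that are significantly associated with treatment group will be covariates in future analyses". It gives no significance level and no list of candidates, and no covariate is fixed in advance here or elsewhere in the document.

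Item 2 fits a treatment-only logistic model to the primary outcome (12-week CO below 8 ppm, yes or no). It then says "Run an adjusted logistic regression adjusting covariates", without naming either model as primary. Item 3 repeats the pair of models for 7-day abstinence at 8 and 12 weeks. There the adjusted 8-week model is worded "Run an unadjusted logistic model with 8-week PPA as the outcome and treatment group as the predictor, adjusting for covariates", which contradicts itself.

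Two other places matter. Section 2.1.3 describes 110 envelopes, "Half of the envelopes indicate that participants are assigned to the control group", and names no stratification factor. Section 2.2 (Research Assistant), Step 3, which precedes randomisation, records that "baseline demographics, smoking habits, and other information will be surveyed". Smoking variables are therefore collected at baseline, although item 1 speaks only of demographic ones.

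**The concern.** A covariate improves a randomised comparison because it predicts the outcome. The plan selects on the other relation, association with treatment, which randomisation makes a matter of chance. Each tested variable then enters with probability equal to the test level, whatever its link to quitting. If nothing is flagged, the adjusted and unadjusted models are the same model.

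The rule also misses imbalances that matter. With 55 per arm, a t-test at 5% needs a difference of about 1.98 × √(2/55) = 0.38 SD. A smaller imbalance in a strong predictor goes unadjusted, while a larger one in an irrelevant variable is adjusted for.

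Two things are at stake: power in a trial of about 110 people, and a primary analysis that can be identified in advance. Selection uses baseline data and allocation, not outcomes. Even so, the content of the adjusted model is unknown until those data are seen, and the plan does not say which of the two primary-outcome results leads.

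**Working it through.** **Inputs from the document.** 110 envelopes, half per arm, so 55 per arm (section 2.1.3); t-test or chi-square screening, then logistic regression (section 2.4). The document has no power calculation to reproduce.

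**Assumed inputs.** The document gives none of these: screening and final tests two-sided at 5%; 10 independent candidates, two of them prognostic; quit rates of 10% vs 30%, 20% vs 45% and 30% vs 55%; no loss to follow-up.

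**Step 1: how often the rule adjusts for anything.** For k independent candidates, P(none flagged) = 0.95^k.

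| k | Adjusted model = unadjusted | At least one chance imbalance flagged |
|---|---|---|
| 5 | 0.774 | 0.226 |
| 10 | 0.599 | 0.401 |
| 20 | 0.358 | 0.642 |

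Any one predictor is omitted with probability 0.95. With two predictors, both are omitted with probability 0.95² = 0.9025. At a 10% screening level the single-predictor figure would be 90%.

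**Step 2: effect on power.** 3000 simulated trials per setting, standard normal candidates, Wald test of treatment. Log odds ratios per SD for the two predictors were 1.0 and 0.6 (strong), 0.7 and 0.42 (moderate), 0.35 and 0.2 (weak), or zero. The Monte Carlo standard error is about 0.7 to 0.8 points.

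| Predictors | Quit rates | Unadjusted | Plan's rule | Two fixed | Fixed minus rule (points) |
|---|---|---|---|---|---|
| Strong | 10 vs 30% | 73.9% | 73.3% | 81.5% | 8.2 |
| | 20 vs 45% | 82.8% | 82.4% | 89.1% | 6.7 |
| | 30 vs 55% | 74.8% | 74.7% | 84.0% | 9.3 |
| Moderate | 10 vs 30% | 74.6% | 74.2% | 79.0% | 4.8 |
| | 20 vs 45% | 81.6% | 81.1% | 84.7% | 3.6 |
| | 30 vs 55% | 75.0% | 75.1% | 80.4% | 5.3 |
| Weak | 10 vs 30% | 76.2% | 75.3% | 76.2% | 0.9 |
| | 20 vs 45% | 80.9% | 80.3% | 81.6% | 1.3 |
| | 30 vs 55% | 75.2% | 75.3% | 77.5% | 2.2 |
| None | 10 vs 30% | 73.9% | 73.3% | 73.2% | −0.1 |
| | 20 vs 45% | 79.7% | 77.9% | 78.7% | 0.8 |
| | 30 vs 55% | 74.8% | 74.3% | 75.5% | 1.2 |

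The strongest predictor was selected in 4.3% to 5.7% of trials and any variable in 39% to 42%, as Step 1 predicts. Wherever there is a predictor, the rule is within 1 point of no adjustment. As a check, a two-proportion formula at 55 per arm gives 75.3% (10 vs 30%) and 80.8% (20 vs 45%), in line with the unadjusted column.

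**Step 3: type I error.** With equal quit rates of 10%, 20% and 30%, rejection under the rule was 2.7%, 4.4% and 5.0% (moderate) and 2.4%, 4.0% and 5.2% (strong). With the fixed pair it was 3.2%, 4.9% and 5.3%, and 3.3%, 4.3% and 5.3%. Neither is inflated. At 10% the Wald test is conservative, slightly less so with the fixed pair, which could explain a little of the gain in the 10 vs 30% rows.

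**Step 4: sensitivity.** A separate simulation with 6 candidates, two or three of them prognostic, gave gains of about 3 to 8 points. At 10 vs 30% the likelihood-ratio test gave similar gains (for example 77.1% to 79.6%, and 77.3% to 85.5%), so they do not depend on the Wald test. Repeats of the 10-candidate simulation ranged over 6 to 10 points (strong), 3 to 7 (moderate) and 0 to 3 (weak).

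**Step 5: what is estimated.** At 20% vs 45% the unadjusted odds ratio is (0.45/0.55)/(0.20/0.80) = 3.27. Conditional on the moderate predictors it is 3.81. The two models estimate different quantities, which is a further reason to name one in advance.

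**The case against.** The strongest reply is that nothing planned is invalid. The unadjusted primary model comes first in item 2, does not depend on the rule, and keeps its error rate. The plan forgoes an optional gain. This is correct, and it limits the weight of the point.

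The size of the gain is also wholly assumed. The upper figures need a predictor with an odds ratio of about 2.7 per SD (log odds ratio 1.0), and weak predictors give a gain close to simulation error. At 10% vs 20%, power goes from 28.2% under the rule to 31.4% with moderate predictors, and from 27.7% to 30.0% with weak ones. With 45 per arm the figures are 22.0% to 24.9% and 20.6% to 22.3%. At 20% vs 60% the gain is under 1 point. A fair overall range is about 0 to 9 points. This also stands, but it does not rescue the rule, which yields essentially no gain however strong the predictors are.

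Item 1 may mean all baseline variables and not only demographic ones. That is possible but hardly matters: barring the prognostic variables from candidacy changed the rule's power by at most 0.4 points.

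This manual supplements an IRB protocol that is not included here, and the test level or the lead model might be stated there. That leaves the explicit rule in section 2.4 untouched.

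Finally, because section 2.1.3 has the research assistant open an envelope at random, a baseline comparison could serve as a check on allocation. That is a fair use of such a test, but it does not justify letting the result decide the model.

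**Conclusion.** The concern holds. The rule chooses covariates by a criterion unrelated to prognosis, so the adjusted analyses have in practice the power of the unadjusted ones. A fixed pair of real predictors would add roughly 4 to 9 points if moderate or strong and 1 to 2 if weak, at the assumed quit rates with 55 per arm and complete data. It would add nothing if the chosen variables do not predict quitting.

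The 95% omission rate rests only on sound randomisation and a 5% screening level. The power figures rest on the assumed quit rates and predictor strengths. This is a loss of efficiency and of pre-specification, not a source of bias or excess false positives. It should be fixed because the better method is available at almost no cost. The unnamed lead model and the contradictory wording in item 3 are secondary, but belong in the same edit.

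**What to change.** - Remove the selection rule and the baseline significance tests from item 1, and keep the descriptive table. If a check on allocation is wanted, label it as that and do not let it feed the models.
- Before any outcome is analysed by arm, fix one or two prognostic baseline covariates, for example cigarettes per day and a dependence or quit-history item if the survey records them. Use them whatever the observed imbalance, in the adjusted models for 12-week CO and for 7-day abstinence at 8 and 12 weeks.
- State which model is primary for the 12-week CO outcome and report the other as supportive. Say that the adjusted odds ratio is conditional and will differ from the unadjusted one.
- Correct item 3 so that the adjusted 8-week model is not called unadjusted.
- Name a fallback for separation, such as Firth logistic regression. In the simulations non-convergence reached at most 0.7%, only at a 10% control quit rate, and about equally in all models.
- For change in smoking quantity, if baseline quantity is recorded, model the follow-up value with the baseline value as covariate.

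The cost is SAP wording, with no new visit, participant or measurement, provided the baseline survey (not included in the document) holds the chosen items. The covariate set must stay small: at a 10% quit rate there would be only about 11 quitters among 110.

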### 2.1.1 Pre-launching

- Before launching the study, the study research assistant will:
  - Approach individuals who attend the HIV clinic at GMU and conduct face-to-face interviews to screen them for eligibility.
  - Get notified by physicians at the clinic of potentially eligible/interested participants so that the RA can conduct face-to-face interviews to screen them for eligibility
  - Get trained on conducting follow-up counseling sessions according to the counseling guide
  - Prepare baseline and follow-up surveys in the same format across participants (via computer, WeChat, in-person etc.)
  - Ensure paper data forms are finalized and computer data entry systems are ready for data entry (EpiData) so that computer-generated spreadsheets of data can be generated
  - The RA will prepare self-help manual and NRT gum for every participant
  - Purchase the CO monitor, train users how to use it for biochemical verification of quitting at 12-month follow-up assessment
  - Train the counselor using the counseling guide that is established to conduct counseling sessions. Counselors should be familiar with the content and procedures of the guide to communicate with participants
  - Counselor should be familiar with referral services around the area/online for smoking cessation

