#### **Step 4: Intervention group (Counseling Sessions and Text Messages)**

- The RA will give each participant in the intervention group a self-help manual and 8-week dosage of NRT gum
- The text messages are going to be sent by the RA following the pre-determined schedule with pre-determined content (Refer to document 6: text messages)
- RA should keep a record of the messages that are sent and have not been sent to each participant (Refer to document 11: tracking spreadsheet)
- RA should keep a record of whether each participant is accepted the NRT gum (Refer to document 11: tracking spreadsheet)

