#### **Step 5: Control group**

- The RA is going to give out a self-help manual and 8-week dosage of NRT gum to participants who are assigned to the control group
- RA should keep a record of whether each participant is accepted the NRT gum (Refer to document 11: tracking spreadsheet)

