#### **Step 6: Follow-up Visits**

- The RA is going to administer the follow-up survey at 8-week and 12-week (Refer to document 4: 8-week survey and document 5: 12-week survey)
- RA has the flexibility to administer the surveys over WeChat or phone if in-person administration is not possible
- The RA is going to make sure that surveys are completed by the participants and have participants' ID number on each survey
- The RA is going to enter ID numbers and responses into EpiData

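### The primary outcome calls a 12-week CO reading below 8 ppm cessation on its own, so a participant who reports smoking in the past week can count as a quitter

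*Combined protocol and SAP*

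**What the plan says.** Section 2.4, item 2, makes exhaled CO at 12 weeks the primary outcome and splits it at 8 ppm: "participants have either a PPM level that is less than 8 (success in cessation"), with 8 or above counted as no success. No other condition is attached. The outcome is compared between arms by logistic regression, unadjusted and then adjusted.

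Item 3 treats abstinence as a different outcome: "Analyze secondary outcomes: 7-day point prevalence abstinence at 8- and 12-week". It has its own models and is not combined with CO.

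Step 7 of the research assistant's procedures calls for measuring "the amount of carbon monoxide in the exhaled air for all participants using a CO monitor", so the test is not limited to people who say they have quit. Section 2.1.1 gives the monitor's purpose differently: "train users how to use it for biochemical verification of quitting at 12-month follow-up assessment".

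**The concern.** Verifying a quit presupposes a reported quit. The primary rule contains none, so it measures a CO level and labels it cessation. Someone who reports smoking within the past week and reads 7 ppm would be a success on the primary outcome and a non-abstainer on the secondary one, in the same dataset at the same time point. The plan does not say how such a conflict is to be read.

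Two things are at stake.

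- **Dilution.** If low-reading smokers are equally common in both arms, the arms look more alike than they are and power is lost.
- **Bias.** If one arm cuts down more without quitting, low-reading smokers accumulate in that arm and the contrast can be exaggerated. Only the intervention arm receives messages and counselling, but both arms receive gum and a manual; for controls the research assistant will "give out a self-help manual and 8-week dosage of NRT gum to participants who are assigned to the control group". The documents do not show that reduction will differ by arm, so inflation is a possibility and not a prediction.

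**Working it through.** The plan gives no event rates, significance level, power target or sample-size derivation, so there is no figure to reproduce. The misclassification follows from the wording alone. The calculation only shows how much it could matter.

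**From the documents:** 110 envelopes, half per arm (section 2.1.3), so n = 110/2 = 55 per arm; success is CO below 8 ppm.

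**Assumed:** no dropout; two-sided 5% test of two proportions (pooled z-test, normal approximation); the true abstinence rate p; f, the share of continuing smokers who read below 8 ppm; d, the share of those low-reading smokers who deny smoking. All true abstainers are taken to read below 8 and to report abstinence.

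**Formulas:**
- CO-only success rate = p + (1 − p)f
- Combined success rate (reported abstinence and CO below 8) = p + (1 − p)fd

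**1. Equal f in both arms, true abstinence 10% against 30%.** At f = 10%: control 0.10 + 0.90 × 0.10 = 0.190; intervention 0.30 + 0.70 × 0.10 = 0.370.

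| f | Control | Intervention | Risk difference | Odds ratio | Power |
|---|---|---|---|---|---|
| 0 | 0.100 | 0.300 | 0.200 | 3.86 | 75% |
| 2% | 0.118 | 0.314 | 0.196 | 3.42 | 71% |
| 5% | 0.145 | 0.335 | 0.190 | 2.97 | 65% |
| 10% | 0.190 | 0.370 | 0.180 | 2.50 | 56% |
| 20% | 0.280 | 0.440 | 0.160 | 2.02 | 42% |

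Exact binomial enumeration puts power within 2 percentage points of each entry. At f = 10%, smokers among the successes number 55 × 0.09 = 4.95 of 55 × 0.19 = 10.45 in control, and 55 × 0.07 = 3.85 of 55 × 0.37 = 20.35 in intervention.

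**2. When unequal f exaggerates the effect.** Same true rates, control f = 10% (control rate 0.190).
- Risk difference: the intervention rate must exceed 0.190 + 0.200 = 0.390, so f > (0.390 − 0.300)/0.70 = 0.129.
- Odds ratio: the odds must exceed 3.857 × 0.190/0.810 = 0.905, a rate of 0.475, so f > (0.475 − 0.300)/0.70 = 0.250.

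**3. No true effect, CO alone.** p = 15% in both arms, control f = 10% (rate 0.15 + 0.85 × 0.10 = 0.235).

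| Intervention f | Intervention rate | Chance of a significant result |
|---|---|---|
| 15% | 0.2775 | 8% |
| 20% | 0.320 | 17% |
| 30% | 0.405 | 48% |

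**4. What the combined definition recovers.** True 10% against 30%, f = 10% in both arms: power is 75% if every low-reading smoker admits smoking (d = 0), 65% if half deny, and 56% (no gain) if all deny.

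**5. What the combined definition can cost.** No true effect (p = 15%).
- Equal f of 5, 10 and 20%, with denial 20% in control and 60% in intervention: false positives 6, 7 and 14%, against 5% for CO alone. At f = 10%, for example, the rates are 0.15 + 0.85 × 0.10 × 0.2 = 0.167 and 0.15 + 0.85 × 0.10 × 0.6 = 0.201.
- f = 10% against 20%: CO alone gives 17%. The combined definition gives 8% if half deny in both arms (0.1925 against 0.235), but 19% if denial is 20% against 60% (0.167 against 0.252).

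**The case against.** The best defence is that CO alone keeps self-report out of the primary result of an open trial. The plan has the research assistant role allocate ("RA is going to randomly open up an envelope to assign participants to either the control or the intervention group"), deliver part of the intervention ("The text messages are going to be sent by the RA following the pre-determined schedule with pre-determined content") and collect the outcome ("The RA is going to administer the follow-up survey at 8-week and 12-week"). If intervention participants are readier to deny smoking to that person, the combined definition brings in a bias that CO alone lacks. This stands: under item 5 of the working it can do worse than the present rule, and the documents do not show which error is larger. It is a reason to keep the CO-only result in view. It does not justify calling an admitted smoker a quitter.

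A second argument is that the 12-week abstinence models already report the other component. They do show disagreement at arm level, but they leave the headline classification unchanged.

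The size is also open to challenge, fairly. At f of 2 to 5% the risk difference moves only from 20 to 19.6 or 19 points, and equal f dilutes the effect without raising false positives. The share of low readers depends on eligibility, and the screening form is not in the text. That 7-day abstinence is self-reported is inferred from its listing apart from CO and from the follow-up surveys; the survey forms are not shown. Finally, this manual supplements an IRB protocol that was not available and may already hold a combined definition.

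**Conclusion.** The concern holds. Applied exactly, section 2.4 counts a participant who reports smoking in the past 7 days as a cessation success whenever CO is below 8 ppm, and nothing else in the available text prevents it. CO below 8 is an imperfect measure of cessation, not a useless one.

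How much this matters is unknown, because it depends on a share of low-reading smokers that the documents do not give. Across the assumed range of 2 to 20%, equal in both arms, power falls from 75% to between 71% and 42%. False-positive inflation needs that share to differ by arm, which is not established. The point should be settled before analysis: it concerns the definition of the primary outcome and costs almost nothing to correct. Confidence is medium, given the unseen screening form, survey forms and IRB protocol.

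**What to change.** - Define primary success as reported 7-day abstinence at 12 weeks and CO below 8 ppm. Count anyone who reports smoking in the past 7 days as not abstinent, whatever the reading.
- Keep CO below 8 ppm alone, and 7-day abstinence alone, as prespecified secondary or sensitivity analyses. Always report the CO-only result beside the primary, because denial to an unblinded research assistant could differ by arm.
- Tabulate CO (below 8, 8 or above) against reported abstinence by arm.
- If the IRB protocol already has a combined definition, align section 2.4 with it.

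The cost is analysis wording only: both variables are already planned at 12 weeks, so no visit, participant or device is added. Success rates will fall somewhat in both arms, and smokers who deny smoking and read low will stay misclassified.

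Two housekeeping points can be handled in the same edit, although the conclusion does not rest on them: state how a participant without a CO reading is classified, and reconcile the 12-month verification in section 2.1.1 with the 12-week measurement in Step 7 and section 2.4.
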